All potential subjects will be patients of [name] and the CHP neurological surgery service, who will decide when and if the patient is medically able to participate in research activities. All research-specific activities will be stopped at the request of the patient, patient's parents, or medical team. It will be made clear to patients and parents that participation is entirely voluntary and that patients or parents may make the decision to discontinue involvement in the study at any time.

Prior to completing research activities described below, participants will complete a 5-minute hearing screening via headphones by providing click responses on a computer. The hearing screening will be completed remotely within the participant's home and will be hosted and accessed on the Gorilla experiment platform ([gorilla.sc](http://gorilla.sc)). The research team will meet briefly with participants via Zoom on a non-recorded video call to provide instructions and guidance on accessing and completing the screening. Participant responses will be recorded directly and saved in a database on the Gorilla platform. This screening will occur prior to sEEG implantation.

Participants will also participate in a brief (~12-15 minute) language screening that evaluates phonological awareness. Participants will listen to single-word or single-letter speech stimuli played from a laptop, and provide verbal responses that require them to add, subtract, or blend sounds within a word. This screening procedure will occur in-patient following sEEG implantation but prior to the activities described below which involve neural recordings.

Neither screening procedure will be used for the purposes of determining eligibility.

Each participant will complete self-paced blocks of stimuli that will first establish a baseline for neural activity and behavioral responses with clear speech, and will then record responses for experimentally manipulated blocks to introduce 1) speech-in-noise and 2) a Canonical-Reverse block to model an "accent." Each block involves listening to sound via earphones and making a categorical decision between initial consonants (/b/ or /p/) by tapping a button to indicate the word heard by the participant.

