All auditory stimuli will be adjusted to a comfortable level for each participant as determined by a calibration process completed by the participant. The blocks can be completed with breaks in between as needed or desired and can occur over the course of the participant's clinical stay in the EMU. All blocks involves listening to sound via earphones and making a categorical decision. Because participation is self-paced, the number of sessions in a day over the total course of an individual's participation will depend on their schedule, health, and motivation to complete research tasks. This period may be up to 10 days, however the patient participant's inpatient stay will not be extended for research purposes.

sEEG electrodes and scalp EEG electrodes will be connected to the study team's recording system before beginning research tasks in order to collect neural recordings specifically for research. The recording system will be disconnected at the completion of each research session. sEEG electrodes will be connected to the EMU's recording system for the duration of each participant's inpatient stay per standard of care.

The study team's recording equipment consists of the software required to present stimuli on MATLAB and record electrical signals from electrodes as well as behavioral responses from subjects. Therefore, no audio or visual recordings will be taken.

The risks and benefits of clinical procedures that are part of the patient's standard of care will be explained in a consent process separate from research activities. Electrode placement and recording are conducted strictly based on a patient's clinical needs and will not be dictated or manipulated by research. Participants will incur minimal additional risk by participating in the behavioral research task. Any risks involved will be explained and documented in the informed consent process and may include fatigue, boredom, or frustration. Research staff will ensure that participants and parents/guardians are aware that participation is entirely voluntary and may stop at any time. Every effort will be made to ensure patient comfort throughout study procedures.

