(**H1**) broadly, the relative perceptual weight of VOT and F0, as measured behaviorally, will be reflected in cortical response, (**H2**) with modulation as a function of baseline perceptual weights, (**H3**) shifts experimentally invoked by a change in listening context by presenting speech in noise, (**H4**) and by introducing an 'accent' that shifts short-term input regularities across VOT and F0. In the latter case, our approach will allow us to test the specific directional hypothesis (**H5**) that F0 perceptual weights in the DBSL paradigm are both exaggerated by Canonical input regularities that cleanly convey a VOTxF0 correlation consistent with English and that F0 perceptual weights are down-weighted upon introduction of a regularity that violates the typical pattern of English (supported by scalp EEG pilot, **Figure A**). Our use of sEEG allows us to evaluate these hypotheses across the supratemporal plane thereby testing the strong, and falsifiable, hypothesis (**H6**) that adaptive plasticity effects are present in HG versus (**H7**) apparent only at higher levels of the cortical hierarchy. Our ability to test these hypotheses is complemented by sEEG electrode placement in cortical regions outside STP (see **Figure 3**) which will support secondary hypotheses and serve as control electrode sites.

The study design is justified our extensive behavioral research demonstrating the feasibility of the project rationale. On the electrophysiological side, our pilot data (**Figures A,3**) demonstrate the feasibility of recording robust sEEG and EEG signals responsive to the acoustic dimensions we manipulate. This will provide clear, informative, interpretable data with which to evaluate the hypotheses listed above.

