Evaluating the Hypotheses: Behavioral Analyses. We will evaluate the behavioral impact of the VOT and F0 acoustic dimensions on classification using *mixed-effects logistic regression* (with patient as a random effect, stimulus VOT and F0 as fixed effects and classification responses as the outcome). Following our prior work,^{14,25-29} perceptual weights for the dimensions will be computed for each patient as the correlation between dimension values and the proportion of *peach* classifications across all stimuli in the VOTxF0 stimulus grid with absolute values of the correlation coefficients normalized to sum to one as an *index of relative perceptual weight* in quiet (Aim 1) and in noise (Aim 2). To examine the impact of a change in 'accent' in the DBSL paradigm, we will use mixed logit models with responses as a function of patient, block, test stimulus F0 and the interaction between block and F0 (Aim 2). Patient will be modeled as a random effect, with the other factors as fixed effects.

Evaluating the Hypotheses: Neural Analyses. We will take a multi-pronged analysis approach. Our pilot data in **Figure 3** demonstrate that *high-y* activity (HGA) is modulated by graded acoustic details across the VOT and F0 dimensions across electrodes placed in the STP. Following the analysis pipeline used in our pilot data analyses, we will specifically examine stimulus-time-locked HGA to the *Test* stimuli, which possess consistent, perceptually-ambiguous VOT and differentiated F0. We have specific, directional predictions (detailed above)

regarding how HGA to F0-differentiated *Test* stimuli will vary according to perceptual weight in behavior. To briefly recap, we expect that HGA to *Test* stimuli will be better differentiated (1) in the Speech-in-Noise compared to the Clear baseline context (because F0 carries greater perceptual weight); (2) in the Canonical, compared to the Reverse, context; (3) in the Canonical, compared to the Baseline Clear Speech context (because stimulus statistics exaggerate the dimension regularity in behavior).

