High-gamma amplitude will be calculated using an approach that utilizes the Hilbert transform. Specifically, the signal will be filtered into 8 subbands, logarithmically spaced between 70-150 Hz. For each subband, we will calculate the amplitude (absolute value) of the analytic signal, which is estimated using the Hilbert transform. Each subband will be normalized to its baseline mean and standard deviation, estimated across trials. The HGA estimate is then the mean across these subbands.

We will use *least-squares linear regression neural encoding models* to investigate relationships between acoustic stimulus dimensions and STP neural responses during the baseline quiet context, in which stimuli sample a 2-d F0 x VOT grid. This approach will allow us to identify the subset of electrodes and temporal windows that encode at least one of these 2 dimensions at baseline; targeted analysis on this subset (described below) will then be used to compare listening contexts.

Encoding model inputs will consist of F0 and VOT, with an output of channel- and time-specific HGA. For a given electrode, individual models will be built using single trial data and a sliding window, allowing us to identify the temporal window relative to stimulus onset that yields significant models. Model quality will be assessed in two ways. First, using models built on all trials, we will calculate the regression *F*-statistic, which determines if any coefficients are significant. This will be compared to null distributions estimated with permutation tests that shuffle data across trials. Second, goodness-of-fit will be assessed for significant models by performing leave-one-out cross-validation and calculating R^2 , the proportion of variance in neural activity explained by the model. Finally, we will assess the relative encoding strength of each acoustic dimension using model coefficient *t*-statistics. In summary, this approach will allow us to identify the timing and anatomical location of F0 and VOT encoding during baseline quiet listening conditions for which dimensions are sampled orthogonally (as in **Figure 1a**).

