To characterize shifts in neural encoding across listening contexts, we will investigate Noise using encoding models and Canonical/Reverse contexts using *cluster-based approaches*.^{32,49} Encoding models will be built from the Noise context for all channels and timepoints, using the same approach as Baseline. If a channel/timepoint is significant in either Baseline or Noise, the F0 and VOT coefficient *t*-statistics will be compared across contexts. We hypothesize that encoding of F0 will strengthen and VOT will weaken in Noise, as measured by changes in *t*-statistic magnitudes across multiple models. Next, we will compare neural responses for each of the two *Test* stimuli (which were embedded in the F0 x VOT grids, **Figure 1a**) between Baseline vs. Canonical and Canonical vs. Reverse. The clustering approach will look only at Baseline significant channels and time windows and involves randomly assigning listening context labels to single-trial data followed by a *t*-test at each time step. Across all permutations, a criterion value will be established for each timepoint (>95% of absolute value of *t*). For each of these permutations, we will next determine whether its value exceeds criterion across timepoints, and for how many timepoints it exceeds criterion (a 'cluster'). For each cluster, *t* values will be summed and assigned to all points in the cluster, with the largest summed cluster value stored for each permutation. This will create a null distribution of 1000 cluster values. We then will establish whether the cluster size calculated across real neural data (organized according to listening context) exceeds the 95% permutation-based cluster values such that $p < .001$ indicates an observed cluster is greater than all permutation-based clusters. Using this approach, we will identify context-dependent shifts in HGA responses, which we predict will reflect observed shifts in perceptual weights. Namely, we hypothesize that HGA responses in F0-encoding channels will be enhanced in the Canonical context relative to both Baseline and the Reverse context.

Rigor and Reproducibility. Analyses will be controlled for multiple comparisons, with sex as a co-variate in our analyses. We will use pre-registration and provide access to all the deidentified source data.

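### The neural analyses leave out the trial's /b/-/p/ response, so a site that codes the choice and not the acoustics can produce the predicted context shifts

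*SAP*

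**What the plan says.** The task (Protocol, Research Activities, item 1) is the same in each block: "making a categorical decision between initial consonants (/b/ or /p/) by tapping a button to indicate the word heard by the participant". The same item says that the recording system will "record electrical signals from electrodes as well as behavioral responses from subjects", so the answer is available trial by trial.

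For the Baseline and Noise contexts (SAP, Evaluating the Hypotheses: Neural Analyses) the regression is specified as follows: "Encoding model inputs will consist of F0 and VOT, with an output of channel- and time-specific HGA". A channel passes the Baseline screen if it encodes either dimension. A channel and time point enter the Noise comparison if either context gives a significant model. The predicted pattern there is a larger F0 t-statistic and a smaller VOT t-statistic.

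For Baseline versus Canonical and Canonical versus Reverse, each Test stimulus is compared between contexts by shuffling context labels over single trials, in channels and windows significant at Baseline. The stated aim is that "we will identify context-dependent shifts in HGA responses, which we predict will reflect observed shifts in perceptual weights".

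The windows are timed from stimulus onset and chosen by model significance. No end point before the response is stated. The only named covariate is sex (SAP, Rigor and Reproducibility). The response appears only as the outcome of the behavioral models.

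**The concern.** The manipulation acts on the link between F0 and the answer. The SAP expects F0 to carry more weight in Noise and in Canonical, and H5 states that "F0 perceptual weights are down-weighted upon introduction of a regularity that violates the typical pattern of English". The Test stimuli have ambiguous VOT, so the mix of answers to one fixed sound is exactly what should move between contexts.

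If a site's HGA differs between the two answers, its mean HGA to that sound moves with the mix, even if the site carries no acoustic information. Sex is constant within a patient and cannot adjust a trial-level model within an electrode. Nothing else in the neural plan separates a change in acoustic encoding from a change in the choice.

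At stake is what a positive site can be said to show. H6 and H7 ask where adaptive plasticity appears, and a choice signal could be counted as plasticity of F0 encoding.

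**Working it through.** The plan gives no figure on this point to reproduce. The check follows one hypothetical site through the planned steps: HGA = d × (answer is *peach*) + noise with SD 1, and no F0 or VOT term. All values of d, the answer probabilities and the trial counts are assumptions.

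**1. Baseline screen.** Assume a 5×5 grid with 8 repeats (200 trials), grid steps coded −2 to 2, and choice logit = 1.5×VOT + 0.5×F0. The two-degree-of-freedom F-test at 5% is passed in about 24%, 56% and 93% of runs for d = 0.3, 0.5 and 0.8. Passing it with a significant F0 coefficient as well happens in only about 4–5%, 9% and 15–17%. Entry is therefore mainly through VOT.

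**2. Canonical versus Reverse, one Test stimulus, one window.** With n trials per context and answer probabilities pC and pR:

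- mean shift = d(pC − pR)
- SE = √{[2 + d²pC(1−pC) + d²pR(1−pR)]/n}
- z = shift/SE
- rejection = Φ(z − 1.96) + Φ(−z − 1.96)

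| Setting | d | pC / pR | n | Shift | SE | z | Rejection |
|---|---|---|---|---|---|---|---|
| Weak | 0.3 | 0.70 / 0.50 | 40 | 0.06 | 0.226 | 0.27 | 6% |
| Middle | 0.5 | 0.80 / 0.50 | 80 | 0.15 | 0.162 | 0.93 | 15% |
| Strong | 0.8 | 0.85 / 0.45 | 80 | 0.32 | 0.167 | 1.91 | 48% |

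Simulation agrees (about 6%, 15–16% and 47–48%).

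**3. The planned cluster permutation test**, simulated with pC = 0.80, pR = 0.50 and d from 0.5 to 1.2, rejects in 8–31% of runs with 40 trials per context and 14–60% with 80. It rejects in 5% when the answer mix is equal and 3% when there is no choice signal. The excess therefore comes from the change in mix.

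**4. Steps 1 and 2 together.** Baseline trials are separate from Canonical and Reverse trials, so with independent noise the rates multiply.

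- Either dimension admits the channel: 0.24×0.06 = 1.4%, 0.56×0.15 = 8.4%, 0.93×0.48 = 45%.
- Significant F0 coefficient required (upper values): 0.05×0.06 = 0.3%, 0.09×0.15 = 1.4%, 0.17×0.48 = 8%.
- A channel with no signal at all: 0.05×0.05 = 0.25%.

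**5. Noise route.** Assume logit slopes (F0, VOT) of 0.6, 3.0 in quiet and 1.5, 1.0 in noise (relative F0 weights 0.13 and 0.62), 200 trials per context and d = 0.8. At the choice-only site:

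- the F-test is significant in 98% of runs in quiet and 83% in noise
- mean F0 t rises from 0.59 to 2.75
- mean VOT t falls from 4.16 to 1.75

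This is the pattern the SAP predicts. A site with fixed F0 coding shows no change (3.58 and 3.57). Over 100–400 trials and d from 0.3 to 0.8, the F0 coefficient is significant in 5–15% of runs in quiet and 13–99% in noise.

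**6. With the response in the model.** In the step 5 setting, mean F0 and VOT t fall to about zero and the F0 coefficient is significant in 4–6% of runs. Permuting within response in the cluster test gives 3–13%, from only 60 runs per setting and so imprecise. The price at a true F0 site in noise (200 trials, slope 0.25 SD per unit F0) is a mean F0 t of 3.01 instead of 3.57, a loss of 1 − 3.01/3.57 = 16%.

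**The case against.** Several points on the other side stand.

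- **Frequency.** A reader might infer that any choice-coding site will be taken for a plastic F0 site. The rates do not support that: the weak case barely exceeds 5%.
- **Screening.** The SAP's closing prediction for Canonical concerns channels that encode F0. Enforced strictly, this excludes most sites admitted through VOT. However, the cluster step as written takes all channels significant at Baseline, and the restriction does not touch the Noise comparison.
- **Test used.** A pooled context-by-F0 contrast would give higher rates (25% in the middle setting, about 75% in the strong one), but the SAP does not plan it. It compares each Test stimulus separately and promises control for multiple comparisons.
- **Direction.** If the two Test stimuli shift in mirror image, a choice site cannot be enhanced for both in Canonical; significant enhancement of both occurred in under 0.1% of simulated runs. It does fit the SAP's looser prediction that the Test stimuli become better differentiated.
- **Location.** It is tempting to say that choice signals lie at higher-level sites and so favour H7. The documents say nothing about where they lie. They mention electrodes outside the supratemporal plane "which will support secondary hypotheses and serve as control electrode sites", without a rule for using them against a choice explanation.
- **Timing.** Response timing is not given, so overlap of the tap itself with the analysis window is an assumption.
- **Adjustment.** Choice may be downstream of F0 coding. In a simulated site with truly plastic F0 coding that drives the answer (assumed values), 12–42% of correct positives lost significance after adjustment. Loss of significance therefore cannot be read as proof of choice coding.

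**Conclusion.** The gap is real: no neural test accounts for the response, although the design aims to change the link between F0 and response. A positive context shift therefore cannot, by itself, be attributed to acoustic encoding.

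At a choice-only site, the single-stimulus Canonical/Reverse test is positive in about 6% to 48% of runs against a nominal 5%. This range rests on assumed choice gain (0.3–0.8 SD), answer probabilities and 40–80 trials per context. Most of this route closes if a significant Baseline F0 coefficient is required. The Noise route remains and can reproduce the predicted pattern in full.

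The documents do not support saying that such sites will routinely be misread, or that the error favours H7. This should be settled in the SAP before analysis; it does not invalidate the design.

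**What to change.** 1. Restrict the Canonical/Reverse cluster test to channels and windows with a significant Baseline F0 coefficient, which matches the SAP's own prediction.
2. For every positive Noise or Canonical/Reverse result, report beside the planned test a version that adds the trial's response as a regressor, or permutes context labels within response. Describe a shift as separable from choice only if it persists. If it does not, report that stimulus and choice coding cannot be separated at that site, and do not label the site choice-related.
3. Where response times are recorded, also report windows that end before the response. This is a sensitivity check on motor activity only, because a choice signal can precede the tap.

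The cost is SAP wording and one extra model per positive channel, on data already recorded. Precision is lost because F0 and choice are partly collinear, and adjustment may remove real effect, which is why both versions are reported.

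### The single-trial encoding models leave each trial's own pre-stimulus high-gamma level in the residual; adding it as a covariate would recover precision to the extent that it predicts the response

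*SAP*

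**What the plan says.** All of this is in the SAP, under Evaluating the Hypotheses: Neural Analyses, unless noted.

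- **Outcome scaling.** "Each subband will be normalized to its baseline mean and standard deviation, estimated across trials". The SAP does not say whether baseline here means an interval before each stimulus or the clear-speech block.
- **Unit of analysis.** "For a given electrode, individual models will be built using single trial data and a sliding window".
- **Predictors.** "Encoding model inputs will consist of F0 and VOT, with an output of channel- and time-specific HGA".
- **Selection test.** From models fitted to all trials, "we will calculate the regression *F*-statistic, which determines if any coefficients are significant". The reference is a permutation null that shuffles across trials.
- **Noise context.** "Encoding models will be built from the Noise context for all channels and timepoints, using the same approach as Baseline". F0 and VOT t-statistics are then compared between contexts at any channel and timepoint significant in either one.
- **Canonical and Reverse contexts.** "The clustering approach will look only at Baseline significant channels and time windows".
- **Covariates.** Under Rigor and Reproducibility: "Analyses will be controlled for multiple comparisons, with sex as a co-variate in our analyses". No trial-level covariate is named anywhere.

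The Protocol (Research Activities, item 1) says that the research recording system is connected before the tasks start and disconnected when each session ends. Power and Sample Size in the SAP derives 25 patients from a behavioral effect and gives no power figure for the encoding models.

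**The concern.** The outcome is HGA on one trial in one channel. The level of that channel just before the stimulus is a natural baseline value of the same outcome, and a recording that runs through the session should contain it. Neither planned step uses it trial by trial. The pooled scaling treats every trial alike, and sex is constant within a patient, so it explains nothing in a per-electrode model. Whatever part of the response is predictable from the pre-stimulus level therefore sits in the residual and lowers each F and t.

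These models act as a gate. A site missed at Baseline is not examined in the Canonical/Reverse cluster tests. It stays in the Noise comparison if it is significant in Noise. The t-statistics compared between Baseline and Noise also come from these models, so residual noise enters that comparison directly.

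**Working it through.** **The plan's own figure.** The 25 patients cannot be reproduced, because the effect size is given only by reference to a figure that is not shown. In a paired design at two-tailed alpha 0.05 and power 0.80, N = 25 implies a standardized effect of (1.960 + 0.842)/√25 = 0.560, or 0.584 by the noncentral t. That concerns the behavioral effect and says nothing about the encoding models.

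**Inputs from the SAP.** Two predictors, hence a numerator with 2 df; single-trial models per electrode and window; scaling pooled over trials.

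**Assumptions, not in the documents.** Rho, the within-block, within-electrode correlation of pre-stimulus HGA with the post-stimulus residual, from 0 to 0.7; 250 trials (100 and 500 give the same power to about 0.001 at alpha 0.05); per-test alpha 0.05, with 0.001 as an illustration of a stricter threshold.

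**Step 1: does the pooled scaling remove the trial level?** With pooled mean m and SD s, trial i in a subband becomes (y_i − m)/s. Since m and s do not vary with i, the correlation between a trial's pre- and post-stimulus values is unchanged. This holds under either reading of baseline.

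**Step 2: effect of the covariate.** Residual variance is multiplied by 1 − rho², so the noncentrality becomes λ/(1 − rho²). Denominator df go from n − 3 to n − 4.

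**Step 3: power.** With 250 trials, 80% power at alpha 0.05 needs λ = 9.75. At rho 0.5, for example, λ becomes 9.75/0.75 = 13.0.

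| rho | 1 − rho² | Site at 80%, alpha 0.05 | Site at 50%, alpha 0.05 | Site at 50%, alpha 0.001 |
|---|---|---|---|---|
| 0 | 1.00 | 80.0% | 50.0% | 50.0% |
| 0.1 | 0.99 | 80.4% | 50.4% | 50.7% |
| 0.2 | 0.96 | 81.7% | 51.7% | 52.9% |
| 0.3 | 0.91 | 83.8% | 54.1% | 56.7% |
| 0.5 | 0.75 | 90.5% | 62.9% | 70.7% |
| 0.7 | 0.51 | 98.0% | 80.4% | 92.1% |

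For an 80% site at alpha 0.05 the gain reaches 5 points at rho of about 0.35. In trials, the planned model needs 1/(1 − rho²) times as many for the same precision: 1.04 at rho 0.2, 1.10 at 0.3 and 1.33 at 0.5.

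**Step 4: simulation.** An assumed 5 × 5 grid with 250 trials, 4,000 runs per setting and F reference distributions. With planned power near 65%, the covariate model gave 64%, 66%, 69%, 77% and 92% at rho 0.1, 0.2, 0.3, 0.5 and 0.7. Subtracting the pre-stimulus value instead gave 39%, 44%, 49%, 63% and 88%. With no effect, rejection rates were 4.2% to 5.8% across all three methods.

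**Step 5: why not subtract.** With equal pre- and post-stimulus variances, subtraction multiplies the residual variance by 2(1 − rho), which exceeds 1 whenever rho is below 0.5. The covariate's factor, 1 − rho², is never above 1.

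**The case against.** The strongest reply is that nothing in the documents shows that rho is large. At rho 0.2 or less the gain for an 80% site is under 2 points, and rho may fall as the sliding window moves away from stimulus onset. The clearest opportunity for slow drift, blocks spread over the inpatient stay, acts between blocks, whereas this point concerns variation within a block. This stands, and it makes the size conditional. A reader might infer that power is definitely lost, or take 0.5 as a typical rho; the documents support neither.

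Other limits also stand:

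- A usable pre-stimulus window is an inference from the recording set-up. No such window or inter-trial interval is described, and details may lie in the pre-registration or the pilot pipeline.
- It is tempting to say that pre-stimulus HGA cannot depend on the coming F0 or VOT. The Protocol (Study Design, item 2) says exposure and test trials are mixed together but does not state that order is randomized.
- The power figures are for one model at an uncorrected threshold. They are not power for any of H1 to H7.
- A reader might infer that a Baseline miss loses the site everywhere. The SAP restricts only the cluster tests to Baseline sites.
- The change needs more specification than one added regressor suggests.

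None of this removes the omission or its direction. If rho is zero, the covariate costs almost nothing.

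**Conclusion.** The point holds as an optional efficiency improvement. The encoding models contain only F0 and VOT, and neither the pooled scaling nor sex accounts for a trial's own pre-stimulus level. Precision is lost in proportion to rho squared: negligible at rho 0.2 or below, about 4 points of power at 0.3 and about 10 at 0.5 for an 80% site at a per-test alpha of 5%. Weaker sites or stricter thresholds gain more at the same rho.

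It would be wrong to read this as a validity error. If stimulus values are unrelated to pre-stimulus state, the planned F test keeps its error rate, and the simulation agrees. The conclusion assumes that a clean pre-stimulus window exists and that stimulus order within a block is random; both need confirming.

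**What to change.** In the Baseline and Noise encoding models:

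1. Fit HGA on F0, VOT and that trial's same-channel pre-stimulus HGA, entered as a covariate and not subtracted. Define the window so that it ends before stimulus onset by more than the filter smear.
2. Judge significance on the 2-df partial F for F0 and VOT. The overall F could otherwise flag a channel for its pre-stimulus term alone.
3. In the permutations, shuffle the (F0, VOT) labels and keep each trial's pre- and post-stimulus HGA paired.
4. Report cross-validated R-squared as the increment over the model with the pre-stimulus term only.
5. Estimate rho from the existing sEEG pilot data, and fix the window and covariate in the pre-registration so that the adjustment is not chosen after results are seen.
6. State whether stimulus order is randomized within block, since the argument that adjustment adds no bias depends on it.

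The cost is one degree of freedom per model and a modest amount of extra analysis specification. No patients or procedures are added, provided that the recording contains the window.
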